Appendix 2: Information for CONSORT flow diagram

Appendix 3: Dummy tables

Table 1: Baseline Characteristics

Table 1: Daseille Characteristics		T
	Sham	Active
Gender - no. (%)		
Male		
Female		
Age (years)		
Median (IQR)		
Chronic comorbid disease - no. (%)		
COPD		
Asthma		
Interstitial lung disease or pulmonary disease		
Ischaemic heart disease		
Diabetes mellitus		
Heart failure		
Liver cirrhosis		
Active cancer		
Peripheral vascular disease		
Current or previous smoker		
Preoperative blood tests results		
Haemoglobin (d/DL)		
Mean (SD)		
Creatinine (µmol/L)		
Mean (SD)		
Cardiovascular medication - no. (%)		
Beta-blocker		
Calcium channel antagonist (e.g. amlodipine/felodipine)		
verapamil/diltiazem		
Doxazosin		
Diuretic		
Statin		
Nitrate		
Anti-platelet agents (aspirin, clopidogrel)		
ACE inhibitor		
Angiotensin receptor antagonist		
Warfarin		
SGLT2 inhibitor		
NOAC		
Other anticoagulant		
Metformin		
Insulin		

Abbreviations: SD, standard deviation; IQR, Interquartile range; COPD, chronic obstructive pulmonary disease.

Table 2: Clinical management

Table 2. Clinical management		
	Sham	Active
NIHSS score on admission		
Troponin on admission (ng/L)		
Thrombectomy technique - no. (%)		
Aspiration		
Clot breakup		
Thrombolysis		
Anaesthetic technique - no. (%)		
General anaesthesia		
Sedation		
Endotracheal tube inserted		
Systolic blood pressure <90 mmHg - no. (%)		
Arrhythmias - no. (%)		
Planned level of care on the first night after MT - no. (%)		
Critical care unit		
Stroke ward		
Repatriated		

Abbreviations: SD, standard deviation; IQR, Interquartile range

Table 3: Adherence to intervention.

Adherence - no. (%)	Sham	Active
Patients with ≥1 treatment deviation		
Total number of deviations		
Number of treatment deviations per patient		
0		
1		
2		
Other deviation		

Table 4: Primary and secondary outcomes for blood pressure variability.

	Sham	Active	P value
Primary outcome			
Systolic BP coefficient of variation			
Secondary outcomes:			
Systolic blood pressure			•
Mean			
Standard deviation			
Coefficient of variation			
Diastolic blood pressure			
Mean			
Standard deviation			
Coefficient of variation			
Heart rate			
Mean			
Standard deviation			
Coefficient of variation			

Table 5: Secondary outcomes for heart rate variability. *Mean (SD)*

	Sham	Active	P value	
Time domain measures				
RR-interval				
SDNN				
RMSSD				
SD HR				
NN				
pNN				
Frequency domain measures				
VLF power				
VLF, peak				
LF, power				
LF, peak				
HF, power				
HF, peak				
DFA1				
DFA2				

Table 6. Process/ exploratory measures.

	ACTIVE	SHAM
NIH Stroke Scale (NIHSS) 24h after mechanical thrombectomy (delta change from admission)		
Health status 7 days after mechanical thrombectomy.		
Alive		
Troponin change from admission (delta change from admission)		

Table 7:Adverse events

Adverse Events - no. (%)	active	sham
Patients with ≥ 1 adverse event		
Total number of adverse events		
Type of adverse event		
Cardiac arrythmia		
Local skin irritation		
Other

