# NIH Stroke Scale (NIHSS) measured before the start of mechanical thrombectomy and 24 hours after the procedure.

NIHSS will be assessed at the following time points by a member of the research team:

- any time point after admission to hospital but before induction of anaesthesia
- 24 hours from start of mechanical thrombectomy

Clinically recorded arrhythmias within the first 24 hours after the start of mechanical thrombectomy Defined as electrocardiograph evidence for cardiac rhythm as determined by the treating clinician either documented in the medical records and/ or recorded by a 12 lead ECG.

Absolute levels of serum high-sensitivity troponin-T levels measured before the start of the first transcutaneous autonomic neuromodulation and at the end of the second transcutaneous autonomic neuromodulation.

Additional blood samples to routine care will be collected to measure serum high sensitivity troponin-T (Elecsys, Roche Diagnostics) levels. Blood samples will be collected at any time after hospital admission but before the induction of anaesthesia and within two hours upon the completion of the second transcutaneous autonomic neuromodulation. The time of completion for transcutaneous autonomic neuromodulation is defined as when the device is switched 'on' and 'off' by a member of the research team. If blood samples are not collected, a protocol deviation will be recorded and data point classified as 'missing'.

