the sample size is derived from data reported from the secondary analysis of the BEST study, which examined blood pressure variability and neurologic outcome after endovascular thrombectomy.[1] An adjusted sample size of 36 patients is required to have a 90% chance of detecting, as significant at the 5% level, a decrease in the coefficient of variation in systolic blood pressure from 15±4mmHg in the sham group to 10±4mmHg in the VAN group [assuming 5% non-compliance rate in each group]

Randomisation procedure

Randomisation will occur before the surgical procedure is due to start. Block randomisation (blocks of 4) will be undertaken (STATA). To enter a patient into the VANS trial, research staff at the site will log on to a secure web-based randomisation and data entry platform hosted by Queen Mary University of London and complete the patient's details to obtain a unique patient identification number and allocation to a treatment group. A patient's treatment group allocation will only be revealed to the person performing randomisation.

4. Analysis methods for VANS

General analysis principles

Analyses will follow the intention-to-treat principle: all randomised patients with a recorded outcome will be included in the analysis and analysed according to the treatment to which they were randomised [2, 3]. Patients will be included in the analysis, regardless of whether the treatment they received was compliant with the protocol. Missing data for baseline covariates to be included in the analysis model will be accounted for using mean imputation for continuous variables and the missing indicator approach will be used for missing data for categorical variables [4, 5].

For the analysis of the primary outcome, each secondary outcome, and all process measures, we will present the following information:

- The number of patients included in each analysis, by treatment group
- A summary statistic of the outcome (e.g. mean (SD), number (%)), by treatment group
- The estimated treatment effect
- A 95% confidence interval for the estimated treatment effect
- A two-sided p-value

For all analyses, a significance level of 5% will be used.

Representativeness of patients

All participating sites have been asked to keep a log of eligible patients not recruited to the trial. Reasons for non-participation will be categorised and summarised. Participation in the trial, treatment allocation and completeness of follow-up will be illustrated by a CONSORT flow diagram [6].

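### No baseline-adjusted model is named for 24 h NIHSS and troponin; where an arm effect is estimated, ANCOVA on the collected admission value should replace raw change

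*SAP*

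**What the plan says.** **What is to be estimated.** SAP section 3 lists NIHSS as secondary outcome 3 and places high-sensitivity troponin within organ dysfunction, secondary outcome 4. SAP section 4 (General analysis principles) asks, for each secondary outcome and all process measures, for "The estimated treatment effect", a 95% CI and "A two-sided p-value". Protocol 14.2 promises crude and adjusted mean differences for continuous endpoints. SAP section 4 also mentions baseline covariates in the analysis model. Neither document names the covariates or the model for these two outcomes.

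**How the results are laid out.** In SAP Appendix 3, Table 6 has the rows "NIH Stroke Scale (NIHSS) 24h after mechanical thrombectomy (delta change from admission" and "Troponin change from admission (delta change from admission". It is titled as process and exploratory measures and has no P value column, whereas Tables 4 and 5 have one.

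**Which baselines exist.** Protocol 6.6 collects admission NIHSS. Protocol Appendix A times that assessment at "any time point after admission to hospital but before induction of anaesthesia" and gives the first troponin sample the same window. SAP Table 2 shows both admission values by arm.

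**Text pointing the other way.** Protocol 14.4 lists NIHSS and myocardial injury among outcomes reported without testing. SAP section 5 says process measures get no formal analysis. SAP section 4 also places troponin under exploratory objectives.

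**The concern.** If SAP section 4 governs, someone must produce an arm difference for both outcomes, and the only layout offered is the change from admission. A change score fixes the slope of follow-up on baseline at 1. Where the true slope is below 1, it over-corrects: an arm that starts worse by chance appears to improve more. Randomisation is 1:1 in blocks, without minimisation and with no stratification factor named (protocol 6.3; SAP section 3), so with 18 patients per arm nothing in the design balances admission NIHSS or troponin.

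At stake are the precision of two secondary estimates and their sensitivity to baseline imbalance. Protocol 13.1 describes this as a pilot to collect data for a larger efficacy trial, so those estimates are likely to be reused.

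**Working it through.** **The plan's own figure.** The SAP states: "An adjusted sample size of 36 patients is required to have a 90% chance of detecting" a fall in the coefficient of variation of systolic pressure "from 15±4mmHg in the sham group to 10±4mmHg in the VAN group", with 5% non-compliance per group. Diluting the difference gives 5 x (1 - 0.05 - 0.05) = 4.5, or 4.5/4 = 1.125 SD. A two-sided t test at 5% then needs 18 per arm (power 0.906), so N = 36 reproduces. That figure concerns the primary outcome only. The documents give no SD, correlation or power for NIHSS or troponin.

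**Inputs for this check.** N = 36 with 1:1 allocation, so 18 per arm (from the documents). Assumed: baseline and follow-up SDs equal to sigma, and correlation rho from 0.3 to 0.9.

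**Formulas.** Both variances are in units of sigma^2 x 2/18.
- Change score: 2(1 - rho).
- ANCOVA: (1 - rho^2) x [1 + 1/(36 - 4)] = (1 - rho^2) x 1.03125. The bracket is the cost of estimating the slope.
- Chance imbalance: if the arms differ by d at baseline, follow-up differs by rho x d on average, so the change differs by rho x d - d = -(1 - rho)d. One standard error of baseline imbalance is sqrt(2/18) = 0.33 SD.

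| rho | Change | ANCOVA | Variance ratio, change/ANCOVA | ANCOVA 95% CI narrower by | Shift in change estimate per one-SE imbalance |
|---|---|---|---|---|---|
| 0.3 | 1.400 | 0.938 | 1.49 | 18% | -0.23 SD |
| 0.5 | 1.000 | 0.773 | 1.29 | 12% | -0.17 SD |
| 0.7 | 0.600 | 0.526 | 1.14 | 6% | -0.10 SD |
| 0.8 | 0.400 | 0.371 | 1.08 | 4% | -0.07 SD |
| 0.9 | 0.200 | 0.196 | 1.02 | 1% | -0.03 SD |

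The two methods break even at rho = 2/1.03125 - 1 = 0.94. Ignoring the slope cost, 36 patients analysed as change are worth 36 x (1 + rho)/2 patients: 27.0 at rho 0.5, 30.6 at 0.7 and 34.2 at 0.9.

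**Simulation check.** In 20,000 trials of 18 per arm at rho 0.5, 0.7 and 0.8, the ANCOVA/change variance ratio was 0.78, 0.88 and 0.94. The change estimate moved by -0.50, -0.30 and -0.19 per unit of baseline imbalance. The ANCOVA estimate moved by less than 0.01.

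**Unequal SDs.** If the follow-up SD is 0.8 to 1.5 times the baseline SD, with rho from 0.3 to 0.9, the large-sample ANCOVA/change variance ratio runs from 0.50 to 0.998. The loss can therefore be large or negligible.

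**The case against.** The strongest reply is that Table 6 is descriptive. It lacks a P value column, and protocol 14.4 and SAP section 5 both say these measures are not formally tested. A reader might infer from Table 6 that the SAP commits to testing raw change. The documents do not support that: such a test follows only if the general principles in SAP section 4 prevail, and neither document says which passage governs. What stands is a contradiction to resolve. It does not remove the gap, because SAP section 4 and protocol 14.2 still call for an arm estimate.

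A reader might also infer that change from admission is the only form planned. It is not. SAP section 4 also reports serial NIHSS scores. Troponin appears as absolute levels in protocol 2.3.2, as a peak in SAP Appendix 1 and as a change in Table 6. Adjustment is promised but left unspecified; it is not excluded.

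Two further replies are fair. At high rho the gain is trivial, but below about 0.94 ANCOVA does not lose under equal SDs, and above that its cost is at most about 3% of variance. For troponin, protocol 14.6 already allows non-parametric methods for serious distributional violations or extreme outliers. That deals with skewness but does not name a baseline covariate.

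**Conclusion.** The point holds in a limited form. For two outcomes that the SAP lists as secondary and requires to be estimated, no baseline-adjusted model is named, and the only results rows are raw changes although the baselines are collected. Under equal SDs and N = 36, comparing raw change costs about 29% extra variance at rho 0.5, 14% at 0.7, 8% at 0.8 and 2% at 0.9. Rho and the SD ratio are assumptions.

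It would be wrong to infer that the change score is biased. Under randomisation it is right on average. The -(1 - rho) term is a shift conditional on the imbalance that happens to occur, and with equal SDs it is smaller than that imbalance and opposite in sign. No power figure is offered for troponin: the documents give nothing to base one on, and a comparison of raw change with log ANCOVA would mix the effect of scale with that of adjustment. The primary outcome and the sample size are not touched.

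**What to change.** 1. State whether NIHSS and troponin are formally compared between arms, so that SAP section 4, protocol 14.4 and SAP section 5 agree.
2. Wherever an arm effect is estimated, name the model. For NIHSS, use linear ANCOVA of the 24 h score on the admission score. For troponin, use linear ANCOVA of the log follow-up value on the log pre-induction value, reported as a ratio of active to sham. Give a 95% CI for each.
3. Keep the two Table 6 changes as descriptive rows and add a row for each adjusted estimate.
4. Settle one troponin definition among absolute levels, peak and change, including the timing of the follow-up sample. Protocol Appendix A ties that sample to the end of the second session, while the SAP puts it at 24 h.

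The cost is SAP wording, a matching clarification of protocol 14.4 if needed, and a few table rows. No new data are required.
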